4.5 Study Visits/Follow-Up

No extra postpartum follow-up visits will be performed.

[figure not shown]
4.6 Withdrawals

Subjects who withdraw from the study will be excluded from further follow-up. Outcomes ascertained up until the time of withdrawal will be reported in intention-to-treat fashion. The patient will be withdrawn from the study if she wishes to discontinue participation. If any of the exclusion criteria listed above are met, or condition changes that leads to inclusion criteria not being met anymore, data collection will be terminated, and the patient will be withdrawn from the study.

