4.2 Operationalization

Randomization:

A confidential computer-generated simple randomization scheme (using STATA 17, Dallas, TX) will be prepared. A randomization log with group assignment, subject name, and medical record number will be used to track the randomization process. Subjects will be randomized in a ratio of 1:1 for low-dose or high-dose oxytocin infusion using the prepared computer-generated randomization scheme. Due to the nature of this intervention, blinding will not be possible. The subject will be included in the analysis by intent-to-treat once the randomization assignment has been made. The trial will be considered completed whenever the final enrollment number is reached. If we need more than the anticipated 170 patients to be enrolled, the trial will be paused, and a protocol addendum will be submitted to the IRB.

Labor and Delivery Unit and Staff:

Several training sessions will occur to notify all staff of the trial and the protocol. The training sessions will include a copy of the protocol, which will also be included in a follow-up email communication. All operations will be reviewed with all staff. The PI will be available for questions. An Epic order will be placed by the provider specifying oxytocin dosing according to the randomization assignment using a prepopulated “Order Set”.

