4.3 Administration of Oxytocin Infusion

The Low Pit group will receive a controlled infusion pump at a proximal port on the peripheral IV line. The infusion will start at 2 milli-units/min and will be increased by 2 milli-units/min every 20 minutes. Maximum rate of infusion is 40 milli-units/min. Oxytocin infusion rate is adjusted to maintain adequate uterine contractions.

The High Pit group will receive a controlled infusion pump at a proximal port on the peripheral IV line. The infusion will start at 6 milli-units/min and will be increased by 6 milli-units/min every 20 minutes. Maximum rate of infusion is 40 milli-units/min. Oxytocin infusion rate is adjusted to maintain adequate uterine contractions.

Additional information regarding management of the oxytocin infusion in both groups:

- Initiation of the oxytocin infusion will be performed by the managing nurse as is standard of care at UTMB.
- The oxytocin infusion may be continued at a lower rate or discontinued at the discretion of the managing obstetric team for the usual obstetric reasons (e.g., changes in fetal heart tracing indicative of fetal distress, uterine tachysystole, suspected oxytocin adverse effects, and patient request)
- Oxytocin dosing may be decreased for uterine tachysystole (defined as >5 contractions/10 min, averaged over 30 minutes(13)) according to our current standard of care guidelines below
 - o Uterine tachysystole with category I FHTs
 - Reposition patient
 - Decrease oxytocin to $\frac{1}{2}$ the current dose
 - If tachysystole persists 15 minutes after the interventions, discontinue oxytocin until contractions return to <5 contractions/10 minutes
 - o Uterine tachysystole with category II or III FHTs
 - Decrease (category II) or discontinue (category III) oxytocin infusion
 - Reposition the patient
 - Give IV fluid bolus as ordered by the obstetric provider
 - Notify obstetric provider
 - Immediate evaluation for category III by obstetric provider
 - Consider amnioinfusion or tocolytics as ordered by the obstetric provider
- Oxytocin infusion may be restarted according to our current standard of care guidelines below
 - o If oxytocin was off for <30 minutes – restart oxytocin at $\frac{1}{2}$ the rate that cause the uterine tachysystole, then increase as ordered
 - o If off for >30 minutes – restart at the initial protocol dose and increase as ordered
 - o If obstetric provider can change the rate of increase as deemed clinically appropriate

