Sample size was calculated based on the determination of superiority. The primary outcome is time in minutes from oxytocin initiation to delivery. For the sample size calculation, based on our prior unpublished data, the primary outcome in the low PIT arm would be 858.6 ± 494.9 mins. Using a difference rate of 25% (High Pit group: 643.9 mins), power of 80% and 2-sided alpha of 0.05,. Final sample size: 170 (85/group). This difference between both methods is clinically significant.

Detailed:

```
power twomeans 858.6 644, sd(494.9) power(0.8)
```

Performing iteration ...

Estimated sample sizes for a two-sample means test

t test assuming sd1 = sd2 = sd
H0: m2 = m1 versus Ha: m2 != m1

Study parameters:

```
alpha = 0.0500
power = 0.8000
delta = -214.6000
m1 = 858.6000
m2 = 644.0000
sd = 494.9000
```

Estimated sample sizes:

```
N = 170
N per group = 85
```

This trial will be registered with Clinical Trials Register (Clinicaltrials.gov) before recruitment is initiated and after IRB approval.

References

6. Obstetric care consensus no. 1: safe prevention of the primary cesarean delivery. *Obstet Gynecol.* 2014;123(3):693-711. doi: 10.1097/01.AOG.0000444441.04111.1d. PubMed PMID: 24553167.

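### Section 4.6 ends follow-up when a woman leaves the study in labor, so her delivery and neonatal outcomes are lost although they are charted

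*Combined protocol and SAP*

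**What the plan says.** Section 4.6 describes two routes out of the study. This point concerns the voluntary one: "The patient will be withdrawn from the study if she wishes to discontinue participation". The consequence is that "Subjects who withdraw from the study will be excluded from further follow-up", and the sentence after that limits reporting to what had been ascertained by the time of withdrawal, which it calls intention-to-treat. The other route in 4.6, for women whose eligibility changes, is a separate matter.

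Section 4.2 sets the analysis rule: "The subject will be included in the analysis by intent-to-treat once the randomization assignment has been made". It also says that blinding is not possible.

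Section 13 (Sample size calculations) defines the endpoint: "The primary outcome is time in minutes from oxytocin initiation to delivery". Sections 3 and 4.4 end participation at delivery.

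Section 4.3 lists reasons for which the obstetric team may lower or stop the infusion, ending with "suspected oxytocin adverse effects, and patient request". It does not call any of these a withdrawal.

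Section 7 names medical records as the source of research material. Section 4.7 adds the neonate's chart, section 4.4 allows chart review to 30 days postpartum, and section 4.5 rules out extra visits. Section 13 gives no allowance for withdrawals and no method for missing outcomes.

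**The concern.** Section 4.2 promises that every randomized woman is analyzed, and 4.6 removes the data needed to keep that promise for any woman who leaves before delivery. Describing the remaining data as intention-to-treat does not help, because no primary value remains to be analyzed.

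The trial is open-label, so the decision to leave may depend on the assigned regimen and on how labor is going. It is plausible, though nothing in the documents shows it, that women with slow or difficult labors would leave more often. If so, the missing times would be the longer ones. Long times missing from the High Pit arm would exaggerate its benefit; long times missing from the Low Pit arm would hide it. The newborns of these women would also drop out of the safety outcomes, which section 4.7 treats as essential. The loss is avoidable, because the study's follow-up after enrollment is chart abstraction.

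**Working it through.** **1. What an exit in labor removes.** The primary value exists only once delivery has occurred, and 4.6 keeps only what was ascertained before the exit. For a woman who leaves between randomization and delivery:

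- time to delivery: not available;
- mode of delivery and all neonatal outcomes: not available;
- outcomes observed during the infusion, such as tachysystole and maximum dose: available only up to the exit.

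**2. The plan's own sample size.** Inputs from section 13: "the primary outcome in the low PIT arm would be 858.6 ± 494.9 mins"; High Pit mean 644 min in the software call; difference 858.6 − 644 = 214.6 min; two-sided alpha 0.05; power 80%.

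- Normal approximation: n per arm = 2 × (1.96 + 0.8416)² × (494.9 / 214.6)² = 83.5, rounded up to 84.
- Exact t-test solution: 84.46, rounded up to 85 per arm, 170 in total. This reproduces the stated figure.
- Power at 85 per arm is 0.803, so there is almost no reserve.

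**3. Loss of information alone.** The documents give no withdrawal rate, so the rates below are assumptions, applied equally to both arms.

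| Loss per arm | Analyzed per arm | t-test power |
|---|---|---|
| 0% | 85 | 0.803 |
| 2% | 83 | 0.793 |
| 5% | 80 | 0.778 |
| 10% | 76 | 0.757 |

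**4. Selective loss.** Assume that k of 85 women leave one arm, none leave the other, and the leavers' times average one SD longer than those of the women who stay. The full-arm mean equals the stayers' mean plus (k/85) × 494.9, so dropping the leavers lowers the arm mean by that amount.

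| k | Shift (min) | Share of 214.6 min |
|---|---|---|
| 2 | 2/85 × 494.9 = 11.6 | 5% |
| 5 | 5/85 × 494.9 = 29.1 | 14% |
| 8 | 8/85 × 494.9 = 46.6 | 22% |

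**5. Losses in both arms.** With similar women leaving both arms, the shifts offset. For 5 exits in one arm and 3 in the other, the net shift is (5 − 3)/85 × 494.9 = 11.6 min, or 5% of 214.6.

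**6. Scale.** The standard error of the difference at 85 per arm is 494.9 × √(2/85) ≈ 76 min. A shift of 29.1 min is about 0.4 of that, and 11.6 min about 0.15.

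**The case against.** A reader might infer that 4.3 and 4.6 contradict each other, with one treating a woman's request as dose management and the other as withdrawal. The text does not support this. Section 4.3 concerns a request about the infusion; 4.6 is triggered by a wish to end participation. A woman who only asks for the oxytocin to be stopped is not withdrawn, and 4.2 keeps her in the analysis. That staff would confuse the two requests is conjecture, so a sentence separating them would only clarify what the plan already says.

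It can also be said that the total loss is inferred. The explicit statement that data collection stops is attached to eligibility-driven withdrawals, and the plan does not define follow-up for voluntary ones. That is fair, but exclusion from follow-up together with the limit to outcomes already ascertained leaves no evident way to record a later delivery time.

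The consent pages are not in the supplied text and may deal with chart use after withdrawal. That cannot be checked, so nothing is claimed about them.

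Few exits may occur. The assumed Low Pit mean is 858.6/60 = 14.3 hours, there are no extra visits, both regimens are described as standard of care, and a woman can have the infusion changed without leaving. Ending collection when a participant leaves is also a defensible way to respect her decision.

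What stands is narrower: 4.6 offers no option to keep chart data with her agreement, and without it the rule in 4.2 fails for the primary outcome.

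**Conclusion.** The point holds in limited form. As written, a voluntary exit during labor leaves no primary, mode-of-delivery or neonatal value, which is inconsistent with the intention-to-treat rule in 4.2 and unnecessary given the chart-based data source.

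Its size is unknown. The shift of about 12 to 47 min rests on three assumptions that the documents neither give nor support: 2 to 8 exits, all from one arm, and times one SD longer. A reader might infer from it that High Pit will look better than it is. The documents do not support a direction, since exits could fall in either arm or in both. With few exits, the effect on power and bias would be small. This is a cheap improvement, not a defect that threatens the trial.

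**What to change.** In section 4.6, state that:

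- a woman who leaves the study is asked whether delivery time, mode of delivery, and maternal and neonatal outcomes may still be abstracted from the charts;
- collection ends only if she declines;
- the reason for leaving and her choice are logged by arm.

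Add one clarifying sentence that stopping or changing the infusion is not withdrawal from the study and that outcomes are still collected. Align the consent form with this wording where it does not already say so.

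The cost is a small amendment to the protocol, consent wording where needed, and one item on the data form. There are no added visits or procedures, and no rule on dosing or clinical care changes. The downside is one more question to a woman in labor, which can wait until after delivery. If she declines, her outcomes remain missing, and the log shows how many such women there are in each arm.

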It is important to determine the optimal method for IOL and AOL, with the goal of the highest percentage of vaginal deliveries within the shortest period, with the lowest maternal and neonatal adverse outcomes. The optimal regimen would have the lowest exposure to all labor interventions. While low-dose oxytocin protocols may result in less uterine tachysystole and resulting fetal distress, studies have shown an increased length of labor, with associated increased rates of chorioamnionitis, fetal infection, and postpartum hemorrhage(11). Low-dose oxytocin protocols have also been associated with an increase in OVD for labor dystocia(10).

On the other hand, high-dose oxytocin has been associated with a shorter length of labor(5, 9, 10, 19) without an increase in cesarean delivery rates(5, 9, 11). It is also associated with lower incidences of postpartum hemorrhage and chorioamnionitis(9, 11). Though data is currently mixed, high-dose oxytocin protocols may be associated with decreased CD for labor dystocia(5), which would spare women from a major abdominal surgery. A shorter total labor duration would translate to a shorter overall hospital admission, ultimately decreasing overall utilization resources. This could then decrease medical costs for labor and delivery and optimize use of hospital staffing and resources. Thus, it is of benefit both patients and providers to further investigate the optimal methods for induction and augmentation of labor with oxytocin infusions based on evidence rather than physician preference.

13. Statistical analysis/Sample size:

Analysis will be performed by intention-to-treat. Univariable and multivariable analysis will be used to describe the population in the study and to identify potential confounding variables. For this analysis, normality will be tested using Shapiro-Wilk method. Demographics and descriptive statistics will be used to provide a profile of the study sample. Data will be either shown as median +/- IQR or mean +/- SDEV. Bivariate tests such as t test, Pearson's chi square, and

Mann-Whitney tests will be used as indicated to identify any key differences in the profiles of subjects across study conditions. Statistical analyses of primary and secondary outcomes between study groups will be performed by multilevel regression analysis accounting for both confounding variables as well as adjusting for any potential intra class correlation that may arise from the study design.

Sample size calculations

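### Section 4.6 stops data collection when eligibility changes, even after randomization, so delivery times and later outcomes can be lost from the intention-to-treat comparison

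*Combined protocol and SAP*

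**What the plan says.** Section 4.6 has four sentences.

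- On follow-up: "Subjects who withdraw from the study will be excluded from further follow-up".
- On what is kept: "Outcomes ascertained up until the time of withdrawal will be reported in intention-to-treat fashion".
- On the woman's own choice: "The patient will be withdrawn from the study if she wishes to discontinue participation".
- On eligibility: "If any of the exclusion criteria listed above are met", or if a "condition changes that leads to inclusion criteria not being met anymore, data collection will be terminated, and the patient will be withdrawn from the study".

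The eligibility sentence carries no time limit.

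Elsewhere the plan commits to intention-to-treat. Section 4.2 (Randomization) states: "The subject will be included in the analysis by intent-to-treat once the randomization assignment has been made". Section 13 (Statistical analysis/Sample size) states: "Analysis will be performed by intention-to-treat". Section 4.2 also says of masking: "Due to the nature of this intervention, blinding will not be possible".

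The sample size part of Section 13 defines the primary outcome as minutes from the start of oxytocin to delivery. Section 4.4 places assessment of maternal outcomes after delivery and extends chart review to 30 days postpartum.

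**The concern.** Intention-to-treat needs two things: each woman is kept in her assigned arm, and her outcome is collected. Sections 4.2 and 13 secure the first. Section 4.6 removes the second for any woman whose eligibility changes, or is found to have been wrong, after assignment. Her delivery time, mode of delivery and later maternal and neonatal outcomes would not be collected, and the documents give no method for handling missing outcomes.

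The loss would be decided after randomization by people who know the assignment, so selection bias is possible. The events that trigger the rule are also serious ones, after which the safety outcomes matter most. Section 4.7 itself stresses that a trial of this kind must assess neonatal outcomes.

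**Working it through.** **Which criteria can trigger the rule after randomization.** Section 6 lists eight exclusion criteria.

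- Four belong to the entry stage by their wording: previous non-mechanical ripening, inability or unwillingness to consent, and the two limited to the time before inclusion (non-reassuring tracing and pulmonary edema).
- Three can first arise later: a contraindication to vaginal delivery, fetal demise, and oxytocin allergy.
- Fetal growth restriction is left unclassified here.
- Among the inclusion criteria in Section 5, vertex presentation can be lost.
- The rule also covers ineligibility that was present at entry but discovered later.

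Ordinary intrapartum cesarean is not a trigger, because Section 4.9 lists primary cesarean as an outcome. A demise that triggers withdrawal is still counted, because outcomes already ascertained are kept.

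**The plan's own figure.** Inputs from Section 13: means 858.6 and 644 min (difference 214.6), SD 494.9, two-sided alpha 0.05, power 80%, 1:1 allocation. The t-test solution is 84.46 per group, rounded up to 85, or 170 in total. The stated sample size reproduces.

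**Possible shift in an arm's mean.** Suppose k of 85 women in one arm lose their delivery time, and their mean differs from that of the other women in the arm by D. The full-arm mean is the mean of the remaining women plus kD/85, so the observed mean is off by kD/85, in either direction. Both k and D are assumptions; the documents give neither.

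| k (share of 85) | D = 494.9 min (one SD) | % of 214.6 | D = 247.45 min (half an SD) | % of 214.6 |
|---|---|---|---|---|
| 1 (1.18%) | 5.82 min | 2.71% | 2.91 min | 1.36% |
| 2 (2.35%) | 11.64 min | 5.43% | 5.82 min | 2.71% |
| 4 (4.71%) | 23.29 min | 10.85% | 11.64 min | 5.43% |

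For scale, the design standard error of the difference between arms is 494.9 × √(2/85) = 75.9 min. The one-SD shifts are therefore 0.08, 0.15 and 0.31 standard errors.

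**Rare outcomes.** If a withdrawn woman would have had the only event in her arm, 1/85 becomes 0/84. The upper limit of the exact (Clopper-Pearson) two-sided 95% interval falls from 6.38% to 4.30%.

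**Power.** The two-sample t-test (noncentral t) has power 80.25% with 85 per arm and 79.78% with 84 per arm.

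**The case against.** The strongest reply is that the sentence was meant for women who become ineligible before randomization. Section 4.1 enrolls women before the infusion is ordered, and the intention-to-treat statements could be read as governing everything after assignment. On that reading this is loose wording and no breach. The reading is possible, but nothing states it, and staff will apply the text. The section also speaks of reporting outcomes in intention-to-treat fashion, which points to women already randomized. The interval before the order does not settle the matter either: Section 4.2 has the order follow the assignment, so part of that interval falls after randomization.

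The second reply is that the triggers are few and the effect is small. This largely stands. Two criteria are limited to the time before inclusion, ordinary cesarean is not a trigger, and no document gives a rate for those that remain. Even a one-SD difference in four women moves an arm's mean by less than a third of a standard error. That limits the severity; it does not make the rule correct.

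The third reply is that continued collection does not recover every primary outcome. A woman who becomes ineligible after assignment and never starts oxytocin has no start time. This is true, but it is a separate gap that needs its own rule. Her mode of delivery and her maternal and neonatal outcomes would still be recovered.

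The last reply is that the rewrite also touches voluntary withdrawal, where the consent text governs. That is why a consent-form check is part of the change.

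**Conclusion.** The concern holds. As written, Section 4.6 ends data collection after randomization for women whose eligibility changes or proves wrong, and this conflicts with the intention-to-treat commitment in Sections 4.2 and 13. Keeping outcomes ascertained before withdrawal does not help the primary comparison, because that outcome does not exist until delivery.

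The conclusion rests on the text. Frequency, size and direction cannot be derived from the documents, and nothing in them shows that losses would differ by arm. The illustrated shifts depend wholly on the assumed k and D and are small beside the design standard error. Selection bias and missing safety outcomes are the issue; power is a minor point. The section should be fixed because the loss is avoidable at little cost.

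**What to change.** Replace the whole of Section 4.6, so that no opposing rule remains, with:

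> Before randomization, a woman who does not meet, or no longer meets, the eligibility criteria is not randomized. After randomization, neither a later change in eligibility nor ineligibility discovered late ends data collection: delivery time, mode of delivery and all maternal and neonatal outcomes continue to be abstracted from the charts of the woman and the neonate, and she is analyzed in her assigned arm. A woman may stop participating at any time; her outcomes continue to be abstracted from the chart unless she withdraws consent to use of her data. If she does, no further data are collected, and outcomes already recorded are reported in her assigned arm. The number of women with each outcome missing, and the reason, is reported by arm.

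The cost is a rewrite of one four-sentence section and a check that the consent form covers chart abstraction after a woman stops participating (the consent pages were not available for review). No visits or data sources are added: Sections 3 and 4.4 already end participation at delivery while charts are reviewed to 30 days postpartum, and Section 4.7 already draws on both charts. Clinical decisions about the infusion are unchanged, and the sample size of 170 stands.
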